Aim 3. We will use a Type 3 Hybrid Design to test the effectiveness of the enhanced implementation strategy (i.e., facilitation) on uptake while also assessing impacts of the intervention on child outcomes. We expect that the effectiveness of WISE on child outcomes will vary by the level of implementation fidelity, and a Hybrid 3 design allows for us to explore this hypothesis (in a preliminary fashion in the proposed pilot study, but in a definitive fashion in the subsequent R01).

RE-AIM provides an evaluation framework to assess key aspects of intervention programs implemented in real-word settings. See Table 1 for a summary of outcome measures that align with RE-AIM. Reach will be reflected by teacher report of the number of realized opportunities for WISE lessons divided by the number of possible opportunities (target = 4 opportunities per child per month). Adoption will be

measured using teacher reports of the number of WISE handouts distributed (target = 2 per child per month), teacher report of the number of WISE lessons and activities presented each month, and assessment of food purchase records to assess frequency of purchase of WISE foods. Further, we will modify and use The Organizational Readiness to Change Assessment (ORCA)⁸⁵ as developed for use with the i-PARIHS framework to assesses change commitment (e.g., We value this change) and change efficacy (e.g., We can keep the momentum going) both prior to and during implementation. For Implementation, our WISE fidelity measure will be used across the school year. The WISE fidelity instrument (See WISE fidelity) is rated on a 1 to 4 scale with 4 representing the highest level of fidelity. Each core component is assessed with 2 items. Average fidelity scores above 3 are considered to reflect adequate fidelity on a component. Additionally, overall scores on the fidelity form are created by summing scores across items (range = 0 – 32). Inter-rater reliability of 85% will be ensured. Finally, acceptability and feasibility²⁶ will be assessed through semi-structured

Table 1. Outcome Measures for Hybrid Trial

Construct	Measures
Reach	Number of ECEs/students impacted
Effectiveness	Child FFQ; Child BMI; Child RRS scan
Adoption	Food purchase records reflecting the number of WISE lessons completed; ORCA
Implementation	WISE fidelity, acceptability, feasibility
Maintenance	Number of teacher maintaining/increasing in fidelity after 6 months

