Study Title: Developing and Testing Implementation Strategies for Evidence-Based Obesity Prevention in Childcare
PI: [name]
Institution: University of Arkansas for Medical Sciences
Support: NIH K01 DK110141-01, Arkansas Biosciences Institute (FUNDED)
NIGMS COBRE Center for Childhood Obesity Prevention (FUNDED)

interviews at two time points: (1) between the Fall and Winter and (2) Winter and Spring fidelity assessments. We will also conduct interviews with champions and directors at enhanced sites at the conclusion of the school year. These interviews will focus on identifying remaining barriers and facilitators to WISE uptake as well as assessing feasibility and acceptability of the implementation strategy (See Director and Champion Interview Guides). Maintenance will be assessed by determining the proportion of teachers that increase or remain the same in adoption and fidelity from the initial assessment (Fall) across the school year (Winter and Spring).

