In addition to these measures collected through the K01 study, the COBRE project will support the addition of ECE Feeding Assessments at mealtimes and a baseline assessment of center climate and context. The K01 protocol only included support to assess fidelity to this core component at WISE lessons, not mealtimes. However, it is possible that ECEs' adoption (or lack thereof) of positive feeding practices at mealtimes may impact the overall effect of WISE on child outcomes. We will add two assessments of ECE Feeding Practices: Table Talk⁷⁹ and the Food Intake module of the Building Mealtime Environments and Relationships (BMER)⁸⁰ inventory. Both measures are suited for live observations to record actual ECE behavior. Table Talk quantifies ECEs' feeding communications and captures the full range of practices (i.e., not prone to ceiling effects). It captures feeding communications that are detrimental (e.g., comments that pressure children to eat more, hurry children to finish, coerce children to eat certain foods) and those that are evidence-based (e.g., direct to internal cues, support food exploration). The Food Intake module of BMER captures adult interactions that support or undermine self-regulation at meals (e.g., "Adults do not praise children for cleaning their plates."). These baseline measures will be collected in the Spring of 2018 across 4 months (Feb- May) (See Combined Mealtime Observation Forms). We will collect three assessments in each classroom to best account for potential variability due to time of year or the menu served. Prior to classroom observations, each teacher will be invited to complete a one page (front and back) survey about characteristics of her center (See Pre-WISE Context Measure). This information will be used to inform stratified randomization to treatment conditions (basic or enhanced).

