An additional secondary outcome of interest is the cost required to deliver the enhanced implementation support. Through the EBQI process, we determined the enhanced condition sites will each have a site-level champion. This champion will be a local leader in WISE implementation. Champions will receive an additional 3 hours of training to equip them to serve in this role. Champions will be supported by external facilitators from the WISE staff. The facilitators will meet with each champion in person at least once per month. Related to estimating the costs of this strategy, facilitators will track their contacts with sites (See Facilitation Log). We will also request tracking of efforts by site champions. (See Champion Log). Finally, we will ask all teachers to report monthly on their use of lesson and enhanced support materials (See Teacher Material Report). Data will be collected either through a secure RedCap Server or using paper and pencil.

Our partnering Head Start agency has 12 sites with 38 classrooms. Classrooms will be randomized to participate in either the basic (i.e., control) or enhanced implementation of WISE. Sites are all within Pulaski County and have a similar demographic make-up of ECEs and families. All families served meet the federal guideline for poverty (e.g., an annual income of \$24,250 for a family of 4). All ECEs will receive basic implementation supports (6-hour training at beginning of school year and monthly newsletter). Those randomized to the enhanced condition will receive the additional package of implementation support strategies developed in Aim 2 on a schedule agreed upon by the EBQI panel (e.g., monthly). These will be delivered by the PI or the research assistant. For both groups, we will collect child data before and after implementation. This will provide us with a matched design to assess comparative effectiveness. For both groups, the 6-hour training will be conducted in collaboration with the USDA-funded Team Nutrition project at UAMS (IRB # 206442). Their exempt training evaluation protocol will be in place. We will extract records from their database specific to our UAMS Head Start attendees, link with other study records, and then de-identify data using our coded ID system.

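### Aim 3 states classrooms as the randomised unit but describes the enhanced arm by site, and its model has no site or stratum term, so the number of randomised units (12 or 38) is unresolved

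*Combined protocol and SAP*

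**What the plan says.** All references are to the combined protocol and SAP.

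- **Unit stated.** Study Design and Procedures, Aim 3: "Our partnering Head Start agency has 12 sites with 38 classrooms", and "Classrooms will be randomized to participate in either the basic (i.e., control) or enhanced implementation of WISE". Study Population, Inclusion, and Exclusion, Aim 3, again names classrooms, 38 of them, as what is randomised. No sentence says that sites are randomised.
- **Arm described by site.** The same Aim 3 design text reports a result of the stakeholder process: "we determined the enhanced condition sites will each have a site-level champion". For the end of the year it adds: "We will also conduct interviews with champions and directors at enhanced sites at the conclusion of the school year".
- **Strata.** Of the teacher survey on center characteristics it says: "This information will be used to inform stratified randomization to treatment conditions (basic or enhanced". The strata are not named.
- **Model.** Data Analysis, Aim 3, specifies multilevel models with fixed terms for intervention and time, and random effects for the clustering of children in a classroom and of repeated observations on a teacher. Neither site nor stratum is listed.

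**The concern.** Enhanced versus basic is the main comparison of Aim 3, and its precision depends on how many units were independently allocated. The text fits three readings:

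- **A. Whole sites allocated.** There are 12 units, about 10 degrees of freedom rather than 36, and the model omits the level at which treatment was assigned.
- **B. Classrooms allocated within sites.** Site is a blocking factor, and omitting it makes intervals somewhat too wide.
- **C. Classrooms allocated regardless of site.** Omitting site leaves type I error about right.

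Under B and C the variance problem goes away, but basic classrooms then sit in the same site as a champion, and the plan does not say how this will be reported.

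Under A the issue bears most on WISE fidelity. Its first round falls in the autumn of the implementation year, so the planned rounds contain no earlier fidelity score to adjust for.

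**Working it through.** The plan gives no significance level, power, ICC, site sizes or allocation ratio for Aim 3, so it has no figure of its own to reproduce.

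**Inputs from the plan:** 12 sites and 38 classrooms, so 38/12 = 3.17 classrooms per site.

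**Assumed:** two-sided 5%; 6:6 sites or 19:19 classrooms; site ICC of classroom means from 0 to 0.20; two site layouts:
- near-even, ten sites of 3 and two of 4: size-weighted mean m = (10×9 + 2×16)/38 = 122/38 = 3.21;
- uneven, sites of 1,1,2,2,2,3,3,3,4,5,6,6: m = 154/38 = 4.05.

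**Step 1, formula under A.** Design effect DE = 1 + (m − 1)×ICC; actual type I error = 2×(1 − Φ(1.96/√DE)).
- Near-even, ICC 0.05 / 0.10 / 0.20: DE = 1.11 / 1.22 / 1.44; √DE = 1.05 / 1.11 / 1.20; error = 6.3% / 7.6% / 10.3%.
- Uneven: DE = 1.15 / 1.31 / 1.61; error = 6.8% / 8.6% / 12.3%.

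**Step 2, simulation.** A t-test on 38 classroom means (36 df) stands in for the planned model. Each setting had 20,000 to 40,000 null trials.

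| Allocation, site omitted | ICC 0 | 0.05 | 0.10 | 0.20 |
|---|---|---|---|---|
| A, near-even | 5.0% | 6.3% | 7.7% | 10.2% |
| A, uneven | 5.2% | 6.6% | 8.2% | 12.2% |
| B, near-even | 5.1% | 4.4% | 4.3% | 3.5% |
| C, near-even | 5.0% | 4.7% | 4.9% | 5.1% |

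Under A, a t-test on 12 site means (10 df) stays between 4.5% and 5.1% in both layouts.

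**Step 3, strata under A (near-even).** Suppose sites were allocated in six matched pairs. At ICC 0.05 / 0.10 / 0.20 the error with site omitted is 6.0% / 6.6% / 8.8% if the matching variable correlates 0.5 with the site effect, and 5.0% / 4.8% / 5.1% if it correlates 0.9. Strong pairing removes the inflation.

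**Step 4, shared sites.** Take a site to have a champion if it holds at least one enhanced classroom. Under C with 19:19 and near-even sites, about 15 basic classrooms lie in three-classroom sites and 4 in four-classroom sites. The expected number sharing a site with an enhanced classroom is 15×(1 − C(18,2)/C(37,2)) + 4×(1 − C(18,3)/C(37,3)) = 15×0.770 + 4×0.895 = 15.1 of 19. Under B it is all 19, provided every site has at least two classrooms. Under A it is none.

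**The case against.** The strongest reply is that the plan says twice that classrooms are randomised and models classrooms. Some of the delivery text also fits that: the added package goes to those randomised to the enhanced condition, in a paragraph that has just spoken of all educators, and it is delivered by study staff. References to enhanced sites could then be shorthand. This stands as far as it goes: whole-site allocation is stated nowhere. It does not settle the matter, because a site-level champion and stratification from center characteristics point the other way, and taking classrooms at face value leaves the shared-site question open.

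Other points, and what remains of them:
- The analysis text may be a summary, with site unmentioned rather than excluded. That is possible, but its stated purpose is to model clustering, and site is a level of clustering that the plan itself describes.
- "Sites are all within Pulaski County and have a similar demographic make-up of ECEs and families". This may keep site ICCs low, but it speaks only of demographics, not of leadership or center climate.
- "For both groups, we will collect child data before and after implementation". If these data are analysed as change, only site variation in change matters. For fidelity, the Spring 2018 mealtime observations are a related baseline that could serve as a covariate, though they are not the fidelity score.
- Aim 3 examines whether child outcomes vary with fidelity only "in a preliminary fashion in the proposed pilot study, but in a definitive fashion in the subsequent R01". Its pilot status lowers the stakes of a type I error but does not remove the need to report the right number of units.

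A reader might infer that the trial really has 12 units and that its intervals will be too narrow. The documents do not support that: it needs whole-site allocation, site clustering, and strata that fail to absorb it.

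**Conclusion.** The inconsistency about the randomised unit is real, and the model as written is not tied to either unit or to the planned strata. This should be fixed. Confidence is high on the text and the missing terms, and low on the size of any effect.

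Too-narrow intervals are a conditional consequence. Under unstratified whole-site allocation, a nominal 5% test runs at about 6%, 8% and 10% for site ICCs of 0.05, 0.10 and 0.20 with near-even sites, and at about 7%, 8% and 12% with uneven ones; at ICC 0 there is no inflation. If classrooms were allocated within sites the intervals are slightly too wide, and if allocated regardless of site the error is about 5%. In both classroom cases most or all basic classrooms share a site with a champion. Any spillover could shrink the contrast, but nothing in the documents allows its size to be estimated. Every ICC, site size and allocation ratio used here is an assumption.

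**What to change.** 1. Reconcile the Aim 3 statements in Study Design and Procedures and in Study Population, Inclusion, and Exclusion to the unit and strata actually used. Report the number of randomised units accordingly (12 or 38).
2. Include the randomisation strata in the Aim 3 models.
3. Treat site according to the unit:
   - **Sites:** use a site-level analysis with a stratum term. Alternatively, use a random site effect with small-sample degrees of freedom, kept in the model even if its variance is estimated as zero. In simulation with near-even, unstratified sites, the estimate was zero in 18% to 54% of trials over ICC 0.20 down to 0. With 10 df this model was conservative, at 2.4% to 4.3%. A Kenward-Roger correction was not simulated.
   - **Classrooms within sites:** include site as a blocking term.
   - **Classrooms regardless of site:** a site term is optional.
4. If classrooms were the unit, report which basic classrooms share a site with a champion.

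**Cost.** Wording and one or two model terms; no new data. If sites were the unit, unstratified site-mean intervals over ICC 0 to 0.20 are about 8–31% wider than those of the model without site when sites are near-even, and about 24–43% wider when they are uneven. As a check on the near-even range, √DE × 2.228/2.028 gives 1.10 at ICC 0 and 1.32 at 0.20. If classrooms were allocated within near-even sites, site as a fixed effect changes interval width by between +6% and −5%.

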A primary goal of this study is to improve use of evidence-based obesity prevention in childcare through development of effective implementation strategies. We will enhance knowledge of how to improve implementation, fidelity, and sustainability in these under-studied locations. Childcare shares some contextual similarities with other locations where implementation research has taken place (e.g., schools and other contexts where “paraprofessionals” provide health-related services); however, we don’t know whether lessons learned apply to childcare. Ultimately, improvements in evidence-based obesity prevention in childcare have the ability to impact 11 million children under age 5 in the US annually.³⁶ It is therefore imperative that we develop and test strategies to maximize implementation and sustainability of these practices.

Objectives

This proposal proposes the following aims:

Specific Aim 1. Identify factors associated with degree of fidelity in a previously developed and tested *basic implementation strategy* of WISE. An explanatory mixed methods approach will use secondary data to identify positive deviance and implementation failures among ECEs in a previous WISE implementation study that observed notable variability in fidelity to best practices for obesity prevention. ECEs from the prior study will be identified from quantitative fidelity observations and invited to participate in qualitative interviews to determine contextual and individual barriers and facilitators to effective implementation.

Specific Aim 2. Develop an *enhanced implementation strategy* to support uptake of the WISE intervention using stakeholder input. Based on results from Aim 1, an Evidence-Based Quality Improvement (EBQI) process¹⁸ will be used to engage stakeholders to develop implementation support strategies consistent with an implementation framework (i-PARiHS) and matched to identified barriers/ facilitators.

Specific Aim 3. Pilot test the impact of the *enhanced implementation strategy* on implementation and child health outcomes using continuous formative evaluation. We will determine whether the enhanced strategy is feasible, acceptable, and demonstrates improved implementation, fidelity, and sustainability using a Hybrid Type 3 implementation design.¹ Further, we will test the hypothesis that better WISE fidelity is positively related to child outcomes (e.g., child fruit and vegetable intake, BMI).

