Aim 2. We will use EBQI to (1) match barriers and facilitators to WISE implementation with potential strategies, (2) tailor strategies to the early childhood context, and (3) finalize the enhanced implementation strategy for WISE. The EBQI Panel will include teachers and directors from representative sites that will implement the enhanced strategy in Aim 3. We will include at least one teacher from previous WISE implementation to have an expert advisor role, providing feedback on feasibility and acceptability of potential enhanced implementation interventions based on prior experiences. We will also recruit parents to inform (a) potential improvements to enhance the link between the classroom and home and (b) strategies to improve assessment of impacts on WISE for future studies (e.g., parent recruitment strategies, collection of genetic/ biological data for possible future moderator/mediator analyses). We expect to recruit an EBQI panel of 10 stakeholders. The EBQI panel will review the data on the evidence-based practices, examine the data collected in Aim 1, and outline suggested implementation strategies. The group will work until we have a mutually agreed-upon, locally-adapted (if necessary) WISE intervention and a set of implementation interventions/tools (our “enhanced” implementation strategy) with accompanying steps on how to deploy them.

We will employ strategies to provide structure to the EBQI process. For example, a concept mapping approach invites stakeholders to rate proposed strategies in regards to their importance and feasibility on a Likert scale (1=not important/feasible, 5 = extremely important/feasible). This approach provides quantifiable information, promotes efficient collection of input, and provides a basis from which to probe the EBQI panel. Meetings are anticipated to last 1-2 hours. We will audio record the

Study Title: Developing and Testing Implementation Strategies for Evidence-Based Obesity Prevention in Childcare

PI: [name]

Institution: University of Arkansas for Medical Sciences

Support: NIH K01 DK110141-01, Arkansas Biosciences Institute (FUNDED)

NIGMS COBRE Center for Childhood Obesity Prevention (FUNDED)

meetings to facilitate later review. Participants will receive \$50 for service at each of the 8 sessions of the panel.

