Building on the Team Nutrition evaluation, we will also conduct surveys of teachers at the end of the school year in both treatment groups. These surveys will be a repeat assessment of measures included in the pre-training survey as well as addition of standardized measures of feasibility, appropriateness, and acceptability,⁹⁵ implementation leadership,⁹⁶ Organizational Readiness for Implementing Change,⁹⁷ the

Study Title: Developing and Testing Implementation Strategies for Evidence-Based Obesity Prevention in Childcare

PI: [name]

Institution: University of Arkansas for Medical Sciences

Support: NIH K01 DK110141-01, Arkansas Biosciences Institute (FUNDED)

NIGMS COBRE Center for Childhood Obesity Prevention (FUNDED)

About Feeding Children assessment,⁹⁸ and educator perceptions of the support they received.⁹⁹ For the enhanced group, we will also include questions on their use of aspects of the implementation strategy. Teachers will have to complete these surveys outside of their work schedule. Therefore, we will pay a \$25 incentive for every returned survey. The surveys are estimated to take 30 to 45 minutes. Given limited success with web-based surveys in this group, we will gather these surveys using paper and pencil.

We will complete fidelity observations three times per year: Fall (Sept – Oct), Winter (Jan – Feb), and Spring (March- April). See WISE Fidelity Form. We will train contract staff to conduct fidelity assessments using videos of previous WISE lessons and ensure 85% reliability is achieved. After the Fall and Winter assessments, we will determine which teachers are achieving fidelity. We will randomly select 5 ECEs to complete semi-structured interviews with study staff on aspects of feasibility and acceptability of the implementation. We will restrict our interviews to ECEs that are not achieving fidelity if 5 are in that category. After analysis of these interviews at each of the two iteration points, we will hold EBQI meetings to review the themes that emerged and the observed fidelity in the classrooms up to that point. With feedback from the EBQI panel, we will use this information to determine shifts needed to improve the enhanced strategy for the remainder of the school year.

Study Population, Inclusion, and Exclusion

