Aim 3. 38 classrooms from our partnering Head Start agency will be randomized to implement the basic WISE strategy used in previous studies or the enhanced WISE strategy developed in Aim 2. Because the program is now adopting the WISE curriculum in all agency classrooms, WISE lessons are a part of normal educational activities. As such, we request a waiver of consent for these observations. In addition, 10 educators will be randomly selected and invited to provide feedback on feasibility and acceptability through semi-structured, open-ended interviews twice during the school year. We are requesting waiver of consent for these interviews as they would be the only document identifying teachers as participants in interviews. We will collect verbal consent on our audio recording. Teachers, directors, and champions will be paid \$25 for the interviews as they will take place outside of center hours.

Additionally, to assess comparative impacts on children, we will record review Body Mass Index (BMI) and Food Frequency Questionnaire (FFQ) data from the agency records at the beginning and end of the school year. We will collect a Resonance Raman Spectroscopy (RRS) assessment from children at the beginning and end of the school year as well. RRS is an optical scan of the hand to assess carotenoid intake from fruits and vegetables. It has been used safely in prior studies with children aged 3 and older. We expect to collect this information from up to 820 children between the ages of 3 and 5.

Risks and Benefits

As in all research, there exists the potential risk to study participants is the potential for loss of confidentiality. Measures to protect the confidentiality of study participants will be implemented as described in the Data Handling and Recordkeeping section below. No physical risks related to participation in this study are foreseen. Some educators may experience discomfort as a result of answering questions that they consider personal in nature. This risk will be minimized by their ability to withdraw from the study

Study Title: Developing and Testing Implementation Strategies for Evidence-Based Obesity Prevention in Childcare
PI: [name]
Institution: University of Arkansas for Medical Sciences
Support: NIH K01 DK110141-01, Arkansas Biosciences Institute (FUNDED)
NIGMS COBRE Center for Childhood Obesity Prevention (FUNDED)
or to refuse to answer any question which makes them uncomfortable.

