Aim 3. We will complete rapid coding of the semi-structured interviews with the selected ECEs at each iteration. This coding will focus on identifying aspects of the implementation feasibility and acceptability. Two coders will complete initial content analysis independently and come together to resolve any differences. These data will be combined with the fidelity data collected and presented to the EBQI panel. Changes or improvements to the enhanced strategy will be driven by these findings and the feedback from the EBQI panel.

At the completion of the study, analyses of Implementation and Effectiveness data will examine the descriptive statistics and examine outliers. Multi-level models (MLM) will be

Study Title: Developing and Testing Implementation Strategies for Evidence-Based Obesity Prevention in Childcare

PI: [name]

Institution: University of Arkansas for Medical Sciences

Support: NIH K01 DK110141-01, Arkansas Biosciences Institute (FUNDED)

NIGMS COBRE Center for Childhood Obesity Prevention (FUNDED)

used to account for the dependence among repeated observations of the same teachers in the same classroom as well as children nested within classrooms. MLM refers to a class of statistical techniques developed to analyze multi-level data structures and appropriately model clustered designs. The models will include a fixed term for intervention (basic versus enhanced) and time. Random effects will be included for the correlation of children within classrooms and the correlation of observations within teacher. This analysis will allow for estimation of variance in child outcomes accounted for by implementation (i.e., level 2) effects.

Ethical Considerations

This study will be conducted in accordance with all applicable government regulations and University of Arkansas for Medical Sciences research policies and procedures. This protocol and any amendments will be submitted and approved by the UAMS Institutional Review Board (IRB) to conduct the study.

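### Do the mid-year teacher interviews need to be confined to the enhanced arm, and not only to low-fidelity teachers, for Aim 3 to be answered soundly?

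*Combined protocol and SAP*

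**What the plan says.** Under Study Design and Procedures, Aim 3, staff establish after the Fall and Winter observations which teachers achieve fidelity and then draw five ECEs at random for interview, with the condition "We will restrict our interviews to ECEs that are not achieving fidelity if 5 are in that category". The themes and the observed fidelity go to the stakeholder (EBQI) panel, after which "we will use this information to determine shifts needed to improve the enhanced strategy for the remainder of the school year". Data Analysis, Aim 3, agrees: "Changes or improvements to the enhanced strategy will be driven by these findings and the feedback from the EBQI panel".

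Study Population, Inclusion, and Exclusion, Aim 3, describes the teacher interviews differently. There, "10 educators will be randomly selected and invited to provide feedback on feasibility and acceptability", on two occasions in the year, and no fidelity filter is mentioned. None of these three places names an arm.

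The aim is stated under Objectives: "We will determine whether the enhanced strategy is feasible, acceptable, and demonstrates improved implementation, fidelity, and sustainability". On who receives the added supports, the design section says "Those randomized to the enhanced condition will receive the additional package of implementation support strategies developed in Aim 2". On the year-end interviews it says "We will also conduct interviews with champions and directors at enhanced sites at the conclusion of the school year".

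**The concern.** The sampling frame seems not to fit its use. Only enhanced-condition teachers receive the added package, and only the enhanced strategy is revised. A basic-arm teacher can describe general obstacles to delivering WISE, but not how the extra supports worked. With five interviews per round, each one given to a basic-arm teacher is a noticeable loss. With equal arms the loss also grows as the enhanced strategy succeeds, because fewer enhanced teachers then remain among the non-achievers.

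The filter raises a second doubt. Whenever five non-achievers exist, no teacher who achieves fidelity is interviewed. The design section nevertheless lists these interviews as an assessment of acceptability and feasibility, and does not repeat the selection at that point. At stake would be the quality of the mid-year revisions and a one-sided reading of how acceptable the strategy is.

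**Working it through.** The plan gives no figure to reproduce. The check is a comparison of the text, followed by an illustration of the most that could be lost.

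**Text.** The case for a both-arm draw rests on the protocol naming an arm wherever it means one. That does not hold up. The design section asks all teachers to report monthly on their use of the enhanced support materials, although only one arm receives them, so an unnamed arm proves little. Naming enhanced sites for the champion interviews is also expected, because only those sites have champions. Nothing says that basic-arm teachers will be interviewed, and the one stated use of the themes points to the enhanced arm.

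**Illustration, if both arms were sampled.** The documents give 38 classrooms and five interviews per round. They do not give the allocation ratio, the number of ECEs per arm or the non-achievement rate, so those are assumed. With *b* basic and *e* enhanced non-achievers:

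- expected basic-arm interviews = 5·b/(b+e)
- P(at most one enhanced teacher) = [C(b,5) + e·C(b,4)] / C(b+e,5)

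For 9/9: 5 × 9/18 = 2.5, and (126 + 9 × 126)/8568 = 1260/8568 = 0.147. For 12/6: 5 × 12/18 = 3.33, and (792 + 6 × 495)/8568 = 3762/8568 = 0.439.

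| Assumed basic/enhanced in the pool | Expected basic of 5 | P(at most 1 enhanced) |
|---|---|---|
| 8/10 | 2.22 | 0.088 |
| 9/9 | 2.50 | 0.147 |
| 10/8 | 2.78 | 0.225 |
| 12/6 | 3.33 | 0.439 |
| 11/4 | 3.67 | 0.593 |
| 8/2 | 4.00 | 0.778 |
| 18/18 (two ECEs per classroom) | 2.50 | 0.169 |
| 24/12 (two ECEs per classroom) | 3.33 | 0.451 |
| 19/19 (no filter) | 2.50 | 0.170 |

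Over two rounds, 9/9 twice gives 2.50 + 2.50 = 5.0 basic-arm interviews of 10. 9/9 followed by 12/6 gives 2.50 + 3.33 = 5.8, and 8/10 twice gives 2.22 + 2.22 = 4.4. With unequal arms and equal non-achievement rates, the basic share is 13/38 = 34% or 25/38 = 66%. If the draw is from the enhanced arm only, every figure is zero.

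**Number of interviews.** The design section implies 5 × 2 = 10. The population section gives 10 if its total covers both rounds, or 10 × 2 = 20 if the same ten teachers are seen twice.

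**Where the interviews enter.** They are coded for themes and shown to the panel. The multilevel models in Data Analysis, Aim 3, are described for the implementation and effectiveness data and do not use the interview themes as an outcome. The panel also sees observed fidelity, and on its membership the Aim 2 design text says "The EBQI Panel will include teachers and directors from representative sites that will implement the enhanced strategy in Aim 3". External facilitators meet each champion at least monthly, which is a further channel from the enhanced sites during the year.

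**The case for a change.** The strongest reply is that staff who follow the text literally would draw from both arms, since the population section opens its Aim 3 account with all 38 classrooms. The year-end surveys and the director and champion interviews come too late to guide mid-year revision. Aim 1, by contrast, deliberately interviews both the highest and the lowest scorers. A short phrase would settle the arm at no cost in interviews or payments if ten interviews are planned.

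Part of this stands. The text is silent on the arm, and the two descriptions of the teacher interviews differ on the filter and possibly on the number. These are drafting slips.

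The rest does not show a fault. The stated topic is the implementation, which both arms carry out, so barriers heard from basic-arm teachers are legitimate input to an add-on package. An enhanced-only draw would give up that input at mid-year. Aim 1 was built to explain variation in fidelity, so it needed both ends of the scale. The mid-year interviews serve formative problem-finding, for which teachers in difficulty are the natural informants.

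**Conclusion.** The concern does not call for a change. The unnamed arm is a gap the investigators can fill sensibly from the stated use of the themes. The differing counts and the unrepeated filter are clerical, and no planned estimate or test depends on them.

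The size is zero under an enhanced-only draw. Under a both-arm draw it is roughly two to four of five interviews per round, but only on assumed splits, and the loss is partly offset by the value of basic-arm input and by the panel's other sources.

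Sampling non-achievers is openly stated and defensible. Aim 3's question on feasibility and acceptability also draws on year-end teacher surveys in both arms, with standardised scales and extra questions for the enhanced group, and on the director and champion interviews at enhanced sites. In the write-up, analysts should state which arm or arms were sampled, how many interviews were held, and that interviewees were chosen for low fidelity whenever the filter applied. Any between-arm statement on acceptability should rest on the year-end survey.
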